4.5.3 Clinical Laboratory Evaluation

4.5.3.1 Hematology and Biochemistry

Summaries for hematology and biochemistry will be presented for each laboratory parameter at each visit. Change from baseline to each post-baseline visit will also be presented.

If values for any of the parameters are below or above the limit of quantification of the assay (BLQ or ALQ), then they will be included in the summary tables at the BLQ or ALQ thresholds.

For post-baseline visits where laboratory samples are repeated, the values from the first non-missing repeat sample taken for the visit, provided it is taken no more than 7 days after the initial sample, will be used. If no values from repeat samples taken within 7 days are available, then the results from the visit sample should be used.

Shift tables for hematology and biochemistry parameters will be constructed, based upon normal ranges and GW toxicity limits (See Section 6), to determine the categorical shifts from core study baseline to each post-baseline visit. Values will be categorized as 'Normal', 'Low' or 'High' based on normal ranges and 'Toxically Low', 'Toxically Normal' or 'Toxically High' based on GW toxicity limits.

An additional table will be produced, summarizing the number of patients with at least one incidence post-Visit 1 of potential Hy's Law case. Potential Hy's Law case is determined by any increase of alanine transaminase (ALT) or aspartate transaminase (AST) to ≥ 3 times the upper limit of normal (ULN) for patients with normal values at core study baseline (or ≥ 3 times core study baseline value for patients with elevated values at core study baseline) and to >2 times the ULN for patients with normal values at core study baseline (or >2 times baseline value for patients with elevated values at core study baseline) in total bilirubin.

All laboratory data will be listed; listings will include limited demographic information about the patient (age, sex, race and weight at core study baseline). Abnormal laboratory values will be listed separately. A further listing will be created for the laboratory reference ranges and toxicity limits.

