Urea (blood urea nitrogen [BUN])			

Investigators at study centers will be notified of safety laboratory test results. All laboratory results will be reviewed and the reports signed by an Investigator. Any results considered to be of clinical significance must be addressed and followed up as clinically appropriate. See [Section 12.8](#) for guidance on evaluation of potential drug-induced liver injury. All laboratory results considered to represent an AE must be documented on the CRF.

Repeat samples will be taken, if required, for clinical follow-up or if the sample is lost or damaged. Any abnormal end of treatment clinical laboratory result of clinical significance must be repeated at regular intervals until it returns to normal, or until an Investigator is satisfied that the abnormality is not related to the IMP and needs no further investigation.

Sample volume requirements and processing procedures will be detailed in a separate laboratory manual. The patient/caregiver must be advised that it may not be safe for the patient to undertake further blood tests within one month of any study-related blood draws and to inform the Investigator if they suffered any blood loss during the one-month period leading up to a planned blood draw.

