10 WITHDRAWAL

In accordance with the Declaration of Helsinki⁷³, the FDA regulations relating to good clinical practice (GCP) and clinical trials^{74,75,76}, the EU Clinical Trials Directive 2001/20/EC⁷⁷ and/or other applicable regulations, a patient has the right to withdraw from the study at any time and for any reason without prejudice to his or her future medical care by the physician or at the institution.

The patient must be withdrawn from the study if any of the following apply:

- Administrative decision by the Investigator, GW, or a Regulatory Authority.
- Pregnancy.
- Protocol deviation that is considered to potentially compromise the safety of the patient.
- Withdrawal of patient consent/assent.
- Withdrawal of parent(s)/legal representative consent.
- Lost to follow-up.
- ALT or AST > 3 × ULN **and** (TBL > 2 × ULN **or** INR > 1.5).
- ALT or AST > 3 × ULN with the appearance of fatigue, nausea, vomiting, right upper quadrant pain or tenderness, fever, rash, and/or eosinophilia (> 5%).
- ALT or AST > 8 × ULN.
- ALT or AST > 5 × ULN for more than 2 weeks.

Note: Prior to withdrawal for the transaminase elevations noted above, the Investigator may choose to confirm the transaminase elevations by repeating the following laboratory tests within 24 to 48 hours: ALT, AST, TBL, INR, % eosinophils, gamma glutamyl transferase and alkaline phosphatase. **Should the above transaminase elevation criteria be confirmed, the patient must be withdrawn from the trial.**

Patients may also be withdrawn from the study for any of the following:

- Patient non-compliance.
- AE which, in the opinion of the Investigator, would compromise the continued safe participation of the patient in the study.
- Any evidence of drug abuse or diversion.
- Suicidal ideation or behavior of type 4 or 5 during the treatment period, as evaluated with the C-SSRS.

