12.8 Potential Cases of Drug-Induced Liver Injury

All investigational centers are required to submit to the GW PVD the laboratory results for any patient after randomization that meet the criteria for the selected laboratory parameters as follows:

- ALT or AST $> 3 \times$ ULN **and** (TBL $> 2 \times$ ULN **or** INR > 1.5).
- ALT or AST $> 3 \times$ ULN with the appearance of fatigue, nausea, vomiting, right upper quadrant pain or tenderness, fever, rash, and/or eosinophilia ($> 5\%$).
- ALT or AST $> 8 \times$ ULN.
- ALT or AST $> 5 \times$ ULN for more than 2 weeks.

These reports must be sent to the GW PVD using the same fax number for SAE reporting within 24 hours of becoming aware of the results. In addition, please send a copy of the patient's baseline laboratory results with all reports to GW PVD.

Abnormal values in AST and/or ALT concurrent with abnormal elevations in TBL that meet the criteria outlined above are considered potential cases of drug-induced liver injury and will be considered as protocol defined criteria for withdrawal and important medical events. The Investigator will arrange for the patient to return to the investigational site as soon as possible (within 24-48 hours of notice of abnormal results) for repeat assessment of ALT, AST, TBL, alkaline phosphatase and gamma glutamyl transferase, detailed history and physical examination. Patients should be followed in this way until all abnormalities have normalized (in the Investigator's opinion) or returned to the baseline state; however, if the above transaminase elevation criteria are confirmed by the first set of follow-up laboratory tests, the patient must be withdrawn from the trial.

Elevations in ALT or AST $> 3 \times$ ULN **or** TBL $> 2 \times$ ULN alone are not considered potential cases of drug-induced liver injury, but will be followed as detailed above, within 72 hours' notice of abnormal results. If the patient cannot return to the investigational site, repeat assessments may be done at a local laboratory and the results sent to GW PVD.

12.9 Notification of Safety Information to Investigators, Regulatory Authorities and Ethics Committees

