13.6.2.2 Clinical Laboratory Data

Clinical laboratory data from Central Laboratory obtained at baseline (Core Studies), screening (OLE Visit 1), during treatment and at the end of treatment and the change from baseline (Core Studies), during and at the end of treatment will be summarized for the safety analysis set using appropriate summary statistics. Categorical shift tables will also be presented, showing the numbers of patients with values outside the normal range at each clinic visit.

In order only to confirm normal hepatic function before OLE dosing commences, an additional blood sample may be taken at Visit 1 to analyze ALT, AST, TBL and INR at a local laboratory. These data will only be used for eligibility determination.

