Appendix 4 Toxicity Criteria for Laboratory Parameters

The toxicity criteria that will be used to identify abnormal laboratory parameters are presented in [Table 10](#) and [Table 11](#).

Table 10 Toxicity Criteria for Biochemistry Parameters

Parameter	Toxicity Decrease	Toxicity Increase
Chloride	≤0.96xLL	≥1.04xUL
Calcium	≤0.89xLL	≥1.16xUL
Sodium	≤0.96xLL	≥1.04xUL
Potassium	≤0.90xLL	≥1.10xUL
Glucose (mmol/L)	≤3.2	≥16
Phosphate	≤0.79xLL	
Cholesterol	≤0.85xLL	≥1.6xUL
ASAT (SGOT)		≥2.6xUL
ALAT (SGPT)		≥2.6xUL
Lactate Dehydrogenase (LDH)		≥2.6xUL
Alkaline phosphatase		≥2.6xUL
Gamma GT		≥2.6xUL
Bilirubin		≥1.26xUL
Albumin	≤0.84xLL	
Total protein	≤0.84xLL	≥1.16xUL
Urea		≥2.6xUL
Blood urea nitrogen (BUN)		≥2.6xUL
Creatinine		≥2.6xUL
Uric acid		≥1.16xUL

UL = upper limit of reference range

LL = lower limit of reference range

Table 11 Toxicity Criteria for Hematology Parameters

Parameter	Toxicity Decrease	Toxicity Increase
Hemoglobin (g/dL)	≤9.4	
Hematocrit (%)	≤28	
Red cell count	≤0.84xLL	
Mean corpuscular volume	≤0.84xLL	≥1.11xUL
Mean corpuscular hemoglobin	≤0.84xLL	
Mean corpuscular hemoglobin concentration	≤0.84xLL	
Platelets (x10 ⁹ /L)	≤74	
Prothrombin time		>1.5xUL
Prothrombin ratio		>1.5xUL
Total white blood cell count (x10 ⁹ /L)	≤2.9	≥21
Total neutrophil count (x10 ⁹ /L)	≤1.36	≥14.7
Segmented neutrophil count (x10 ⁹ /L)	≤0.75	≥12.3
Eosinophils (x10 ⁹ /L)		≥1.5
Basophils (x10 ⁹ /L)		≥0.31
Monocytes (x10 ⁹ /L)		≥2.1
Lymphocytes (x10 ⁹ /L) for patients <18 years (auto hematology)	≤1.0	
Lymphocytes (x10 ⁹ /L) for patients <18 years (manual hematology)	≤0.2	
Lymphocytes (x10 ⁹ /L) for patients ≥18 years	≤0.2	

Parameter	Toxicity Decrease	Toxicity Increase
Promyelocytes		≥1.1
Metamyelocytes (x10 ⁹ /L)		≥1.1
Mycloocytes (x10 ⁹ /L)		≥1.1

UL = upper limit of reference range LL = lower limit of reference range

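### A liver test repeated because it was high can be replaced by its repeat, and no planned laboratory table then shows that the toxicity limit was passed

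*SAP*

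**What the plan says.** SAP 4.5.3.1 sets one rule for all hematology and biochemistry parameters. When a post-baseline sample is repeated, the analysis takes the "values from the first non-missing repeat sample taken for the visit, provided it is taken no more than 7 days after the initial sample". The visit sample is used only if no such repeat exists.

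Protocol 9.1.9 gives two kinds of reason for repeating: "Repeat samples will be taken, if required, for clinical follow-up or if the sample is lost or damaged". Protocol 12.8 adds a specific one. ALT or AST above 3 x ULN, or total bilirubin (TBL) above 2 x ULN, occurring alone, "are not considered potential cases of drug-induced liver injury, but will be followed as detailed above, within 72 hours" of notice of the result. For the transaminase withdrawal criteria, protocol 10 makes confirmation optional: "the Investigator may choose to confirm the transaminase elevations by repeating the following laboratory tests within 24 to 48 hours".

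SAP Appendix 4 begins "The toxicity criteria that will be used to identify abnormal laboratory parameters are presented in" its Tables 10 and 11. Table 10 puts the upper toxicity limit at 2.6 times the upper limit of the reference range for ALT and AST, and at 1.26 times for bilirubin. The planned biochemistry tables are by-visit summaries (13.1.2), by-visit shifts on reference ranges (13.2.2), by-visit shifts on toxicity limits (13.3.2) and potential Hy's Law cases (13.4).

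**The concern.** A lost or damaged sample leaves no usable original, so substituting the repeat costs nothing. A repeat ordered for clinical follow-up is different: the original is a valid result, and it was repeated because of what it showed. The SAP treats the two alike.

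For liver tests the trigger for retesting lies above the limit used for tabulation, so the substitution works in one direction for the test that prompted it. Laboratory parameters are one component of the primary endpoint, beside the AE profile, and the analysis is purely descriptive. How many patients ever passed a liver limit is therefore something the tables should show. For vital signs and ECG (SAP 4.5.8.1 and 4.5.8.2) the SAP plans counts of patients with at least one flagged post-baseline value. It plans none for a single liver test.

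**Working it through.** The plan has no figure of its own to reproduce here. The inputs are the repeat rule (SAP 4.5.3.1), the retest triggers (protocol 12.8) and the toxicity limits (SAP Appendix 4, Table 10). Section 4.5.3.1 points to Section 6 for those limits, but Section 6 is the reference list.

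**Step 1: direction.** The triggers exceed the limits: 3 > 2.6 for ALT/AST and 2 > 1.26 for TBL. A triggering original is therefore already Toxically High and contributes 1 to its visit in Table 13.3.2. After replacement it contributes 1 if the repeat is at or above the limit and 0 otherwise. The change is 0 or -1, never +1.

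**Step 2: fall needed.** To leave Toxically High, the fall must exceed 1 - limit/original. To leave High in Table 13.2.2 as well, the repeat must be back within the reference range, a fall of 1 - 1/original.

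| Original (x ULN) | Leaves Toxically High | Leaves High |
|---|---|---|
| ALT/AST 3 | 1 - 2.6/3 = 13.3% | 1 - 1/3 = 66.7% |
| ALT/AST 4 | 1 - 2.6/4 = 35.0% | 1 - 1/4 = 75.0% |
| ALT/AST 5 | 1 - 2.6/5 = 48.0% | 1 - 1/5 = 80.0% |
| ALT/AST 8 | 1 - 2.6/8 = 67.5% | 1 - 1/8 = 87.5% |
| TBL 2 | 1 - 1.26/2 = 37.0% | 1 - 1/2 = 50.0% |

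For a fall between the two columns, the patient is still shown as abnormal and only the degree is lost.

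**Step 3: the rule applied to hypothetical values (x ULN).**

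| Test | Original | Repeat | Analysed | Toxically High? |
|---|---|---|---|---|
| ALT | 6.0 | 2.5, day 3 | 2.5 | no |
| ALT | 9.0 | 2.5, day 2 | 2.5 | no |
| ALT | 3.2 | 2.0, day 3 | 2.0 | no |
| TBL | 2.2 | 1.2, day 3 | 1.2 | no |
| ALT | 6.0 | 5.5, day 3 | 5.5 | yes |
| ALT | 6.0 | 2.5, day 8 | 6.0 | yes |
| ALT | 6.0 | none | 6.0 | yes |

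All seven originals passed the limit, but only three are counted. The cases illustrate the rule and say nothing about how often it bites.

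**Step 4: the other tables.** Tables 13.1.2 and 13.2.2 are also by visit and use the analysed value. Table 13.4 counts patients with at least one occurrence, but it needs ALT or AST and bilirubin raised, so an isolated rise cannot appear there.

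**Step 5: timing.** The 7 days run from the initial sample, whereas protocol 12.8 counts from notice of the result. A repeat at the 72-hour limit falls inside the window only if notice came within 7 - 3 = 4 days of sampling; at a 48-hour limit, within 7 - 2 = 5 days. The documents do not give laboratory turnaround.

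**Step 6: scope.** The one-way result applies only to the test that triggered the retest. Other tests on the same panel can move either way. A discretionary repeat of a value below the limit can add a count: an ALT of 2.0 x ULN enters Toxically High after a rise of 2.6/2.0 - 1 = 30.0% or more.

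**The case against.** The strongest reply is that little is hidden. All laboratory data are listed, and abnormal values are listed again by patient and by parameter (Listings 13.1.1, 13.1.2.1 and 13.1.2.2), so every replaced original can be read. Protocol 12.1.1 includes abnormal laboratory findings in its AE definition, and 9.1.9 says "All laboratory results considered to represent an AE must be documented on the CRF". Results meeting the four criteria in 12.8 go to pharmacovigilance within 24 hours. This stands. It narrows the gap to the laboratory tables and to the degree of elevation. It does not close it: a listing is not a count, and entry into the AE tables depends on the investigator's judgement.

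Second, replacement may not occur. The SAP does not define when a repeat is taken for a visit. Its Table 2 has no label for unscheduled visits, while protocol 16.3 mentions event names for unscheduled visits or retests. Under 12.8, if the patient cannot return to the site, "repeat assessments may be done at a local laboratory and the results sent to GW PVD", but protocol 13.6.2.2 summarizes "Clinical laboratory data from Central Laboratory obtained at baseline (Core Studies), screening (OLE Visit 1), during treatment and at the end of treatment". This also stands, and it makes the point conditional.

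Third, protocol 13.6.2.2 itself asks for by-visit shift tables, and using a repeat is a defensible convention. That is a good reason to leave the by-visit rule alone, but it does not argue against adding a worst-value count.

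A reader might also infer that potential Hy's Law cases are lost. The documents do not support that. The text for Table 13.4 refers to any increase and at least one incidence after Visit 1, which reads naturally as all samples, although the SAP does not say so outright. Its use of baseline multiples differs from 12.8 but is a design choice, not an error.

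**Conclusion.** The concern holds in a limited, conditional form. If a retest prompted by an isolated liver elevation counts as taken for the visit, is in the analysis database and falls within 7 days of sampling, then for that test Table 13.3.2 can only keep or lose the patient, and no other planned laboratory table records that the limit was passed. The loss concerns elevations whose first repeat is below the limit; those confirmed on repeat stay counted.

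A reader might infer that the plan conceals liver signals, or that rates in the laboratory tables are materially understated. Neither follows. Most of the falls in Step 2 leave the patient visible as High. The documents also give no elevation rates, within-patient variability or laboratory turnaround, so the number of patients affected is unknown. How long such elevations last is not stated either, so it cannot be said whether a neighbouring visit would show them. This is a minor reporting gap in one component of the primary endpoint.

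**What to change.** Keep the by-visit repeat rule and add one table to SAP 4.5.3.1 and the list of tables:

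> Number of patients with at least one post-Visit 1 value of ALT, AST or TBL at or above the Appendix 4 toxicity limit, and with ALT/AST > 3, > 5 and > 8 x ULN or TBL > 2 x ULN, using the worst value per patient across all scheduled, unscheduled and repeat samples in the analysis database, including initial values later repeated.

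This matches the form already planned for vital signs and ECG and needs no new data. Under it, all seven cases in Step 3 would be counted. The cost is one extra table. Displayed elevation rates will be somewhat higher because they include elevations not confirmed on repeat, and a footnote should say so. Local-laboratory repeats that are not in the database will not be covered.

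Two further changes are not needed. Taking ALT, AST and TBL from the scheduled sample while the rest of the panel comes from the repeat would mix two sampling dates within one visit. A fixed-ULN count beside Table 13.4 goes beyond the gap identified here.

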--	---

	
re-assessed, defined as any of the following:
 
 - ALT or AST > 5 × upper limit of normal (ULN). - ALT or AST > 3 × ULN and (TBL > 2 × ULN or INR > 1.5). - ALT or AST > 3 × ULN with the presence of fatigue, nausea, vomiting, right upper quadrant pain or tenderness, fever, rash, and/or eosinophilia (> 5%). 
If the Core Study ‘End of Treatment’/‘End of Taper Period’ visit assessments or Visit 1 re-assessments (as applicable) raise any safety concerns, the Investigator should consider whether it will be appropriate for the patient to continue to participate in the OLE study, or if the patient should be withdrawn.

Criteria for Withdrawal
	
The patient must be withdrawn from the study if any of the following apply:
 
 • Administrative decision by the Investigator, GW, or a Regulatory Authority. • Pregnancy. • Protocol deviation that is considered to potentially compromise the safety of the patient. • Withdrawal of patient consent/assent. • Withdrawal of parent(s)/legal representative consent. • Lost to follow-up. • ALT or AST > 3 × ULN and (TBL > 2 × ULN or INR > 1.5). • ALT or AST > 3 × ULN with the appearance of fatigue, nausea, vomiting, right upper quadrant pain or tenderness, fever, rash, and/or eosinophilia (> 5%). • ALT or AST > 8 × ULN. • ALT or AST > 5 × ULN for more than 2 weeks. 
Note: Prior to withdrawal for the transaminase elevations noted above, the Investigator may choose to confirm the transaminase elevations by repeating the following laboratory tests within 24 to 48 hours: ALT, AST, TBL, INR, % eosinophils, gamma glutamyl transferase and alkaline phosphatase. Should the above transaminase elevation criteria be confirmed, the patient must be withdrawn from the trial.
 
Patients may also be withdrawn from the study for any of the following:
 
 • Patient non-compliance. • AE which, in the opinion of the Investigator, would compromise the continued safe participation of the patient in the study.

	
 Any evidence of drug abuse or diversion. Suicidal ideation or behavior of type 4 or 5 during the treatment period, as evaluated with the C-SSRS.

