13.1 Sample Size, Power and Significance Levels

As this is an open label safety study, there is no formal sample size calculation. All patients who wish to continue on IMP from the populations included in the double-blind Phase 2 and Phase 3 Core Studies in DS and LGS will be eligible for inclusion. Approximately 680 patients will be enrolled.

All data collected during this study will be summarized across time, using appropriate descriptive statistical methods. There will be no formal hypothesis testing.

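### SAP Table 13.4 counts Hy's Law cases on a baseline-multiplied rule, so some patients who meet the protocol's ULN-based definition of potential drug-induced liver injury are not counted in it

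*SAP*

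**What the plan says.** **SAP 4.5.3.1** plans a table of patients with at least one potential Hy's Law case after Visit 1 (Table 13.4 in SAP Appendix 5, supported by Listing 13.1.4). For a patient with normal values at Core baseline, the transaminase condition is "any increase of alanine transaminase (ALT) or aspartate transaminase (AST) to ≥ 3 times the upper limit of normal (ULN"), joined to TBL above 2 × ULN. For a patient with raised values at Core baseline, the limits become 3 "times core study baseline value for patients with elevated values at core study baseline" for ALT or AST, and more than 2 "times baseline value for patients with elevated values at core study baseline) in total bilirubin". INR is not part of the rule, and nothing is said about the two rises coming from the same sample.

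**Protocol Section 10** (and the synopsis) requires withdrawal under any of four liver criteria, all in multiples of ULN and none adjusted for baseline:
- "ALT or AST > 3 × ULN and (TBL > 2 × ULN or INR > 1.5");
- ALT or AST above 3 × ULN with listed symptoms or eosinophilia;
- "ALT or AST > 8 × ULN";
- "ALT or AST > 5 × ULN for more than 2 weeks".

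The investigator may repeat the tests first. If the repeat confirms the finding, withdrawal is mandatory.

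**Protocol 12.8** lists the same four criteria for reporting laboratory results to pharmacovigilance. Its defining sentence is narrower: ALT or AST abnormalities "concurrent with abnormal elevations in TBL that meet the criteria outlined above are considered potential cases of drug-induced liver injury". It adds that a transaminase above 3 × ULN, or TBL above 2 × ULN, on its own is not such a case.

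**The concern.** Laboratory safety is part of the primary endpoint, and liver injury is the risk for which the protocol sets the most detailed withdrawal rules. A reader will take Table 13.4 as the study's summary of serious liver signals, because no other planned table combines liver criteria. If its rule differs from the protocol's, the report could show few or no cases while patients are being withdrawn under the protocol's own liver criteria, and nothing in the SAP would tell the reader why.

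The missing same-sample condition could work the other way. Treatment can last up to 208 weeks, and the SAP does not say whether an ALT rise and a TBL rise at different visits make one case.

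**Working it through.** The plan gives no liver-event rate, expected count or design figure to reproduce (Protocol 13.1: "As this is an open label safety study, there is no formal sample size calculation"). The check sets the two rules side by side in multiples of ULN.

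**Thresholds.** Let Core baseline ALT or AST be b × ULN and Core baseline TBL be c × ULN.
- SAP 4.5.3.1: ALT/AST ≥ 3 if b ≤ 1, otherwise ≥ 3b; TBL > 2 if c ≤ 1, otherwise > 2c.
- Protocol 12.8: ALT/AST > 3 and TBL > 2, for every b and c.

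The values of b and c below are assumptions.

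| Core baseline (× ULN) | SAP ALT/AST limit | Protocol ALT/AST limit | SAP TBL limit | Protocol TBL limit |
|---|---|---|---|---|
| normal | 3.0 | > 3 | > 2.0 | > 2 |
| 1.2 | 3.6 | > 3 | > 2.4 | > 2 |
| 1.5 | 4.5 | > 3 | > 3.0 | > 2 |
| 2 | 6.0 | > 3 | > 4.0 | > 2 |
| 3 | 9.0 | > 3 | not shown | > 2 |

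The SAP limit equals the protocol's stand-alone 8 × ULN criterion when 3b = 8, that is b = 8/3 = 2.67. Above that baseline, Table 13.4 asks for more ALT (and raised TBL as well) than the protocol needs to withdraw on ALT alone.

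**Illustrative patients** (assumed values, × ULN except INR; values not shown are normal):

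| Patient | 12.8 potential liver injury | Section 10 withdrawal criterion | Counted in Table 13.4 |
|---|---|---|---|
| Normal baseline, ALT 4, TBL 2.5 | yes | yes | yes |
| Baseline ALT 2, then ALT 5, TBL 2.5 | yes | yes | no (needs 6) |
| Baseline ALT 1.5, then ALT 4.4, TBL 3 | yes | yes | no (needs 4.5) |
| Baseline TBL 1.2, then ALT 4, TBL 2.3 | yes | yes | no (needs > 2.4) |
| Normal baseline, ALT 4, TBL 1, INR 1.8 | not clearly | yes | no |
| Normal baseline, ALT 9, TBL 1 | not clearly | yes | no |
| Normal baseline, ALT exactly 3, TBL 2.5 | no | no | yes |

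Rows 2 to 4 are the core of the point: they satisfy the protocol's own defining sentence and are not counted. Rows 5 and 6 do not depend on a raised baseline, but they meet withdrawal and reporting criteria rather than the defining sentence. The last row is a small difference in the other direction (≥ 3 against > 3).

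**Other outputs.** The toxicity shift tables take one parameter at a time, with a single upper limit of 2.6 × UL for ALT and AST (SAP Appendix 4). They cannot separate 3, 5 and 8 × ULN or link ALT to TBL. The adverse events of special interest (SAP Appendix 1) cover abuse liability only.

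**Repeat samples.** SAP 4.5.3.1 uses the first repeat within 7 days in place of the visit sample. If that rule also governs Table 13.4, a lower repeat would remove an initial value that was reportable under 12.8.

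**The case against.** **The rules serve different purposes.** Sections 10 and 12.8 govern the handling of individual patients. Protocol 13.6.2.2 plans laboratory summaries, changes from Core baseline and shift tables, and promises no count of the 12.8 criteria. Table 13.4 is an added summary, and SAP 4.7 says that additions are not detailed there. A baseline-referenced rule also suits a primary endpoint defined as change from Core baseline. This stands: the Hy's Law row is not wrong in itself, and a reader who inferred that the SAP had altered a planned protocol analysis without declaring it would be going too far.

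**Not every withdrawal criterion is called liver injury.** A reader might infer that Table 13.4 misses INR-only, above 8 × ULN or sustained above 5 × ULN cases that the protocol defines as drug-induced liver injury. The documents do not support that. The defining sentence in 12.8 names TBL only, and the next paragraph sets isolated elevations apart.

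**The patients are not lost.** They can appear in the shift tables (ALT > 3 × ULN exceeds 2.6 × UL, and TBL > 2 × ULN exceeds the 1.26 × UL limit), in the abnormal-value listings, and in the withdrawal, adverse event, serious event and discontinuation tables. This also stands. What is missing is the combined count.

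**The data may not support every row.** The central panel (Protocol Table 9.1.9-1) lists prothrombin time, not INR. The Visit 1 local INR serves eligibility only. Some repeats may be local. After Week 48, scheduled visits are 24 to 28 weeks apart, so a two-week sustained rise can be seen only in extra samples. These limits belong in the fix.

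**A raised baseline is not documented.** The protocol advises considering liver monitoring during titration for patients on antiepileptic drugs linked to liver injury. It does not say that they had raised Core baselines, so the table cannot be said to miss that group in particular.

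**Conclusion.** The point holds in a limited form. For patients with raised Core baseline values, the Table 13.4 limits rise to 3b × ULN for ALT/AST and 2c × ULN for TBL. A patient can then meet the protocol's definition of potential drug-induced liver injury, and its withdrawal rule once confirmed, without being counted. Separately, no planned table counts the protocol's other liver withdrawal criteria, and the SAP leaves concurrency unstated.

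The number of patients affected cannot be computed. Neither document gives the Core baseline distribution of ALT, AST or TBL, or the Core Studies' hepatic entry limits. The examples show where the rules part, not how often; baselines above 2.67 × ULN may be rare or absent. It would be too strong to infer that two ALT and TBL peaks months apart will be counted as one case: the SAP neither requires the same sample nor expressly allows different ones.

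There is no hypothesis test, and no conclusion is shown to change. This is an inexpensive improvement to the reporting of the primary safety endpoint, not a fault that invalidates the analysis.

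**What to change.** In SAP 4.5.3.1, Table 13.4 and Listing 13.1.4:

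1. Keep the current Hy's Law row, label it as baseline-referenced, and state that ALT/AST and TBL must come from the same sample.
2. Add a row for ALT or AST > 3 × ULN with TBL > 2 × ULN in the same sample, regardless of baseline.
3. Add a row for each other criterion in Protocol 10 and 12.8 as far as the collected data allow: INR where it is recorded or can be derived from prothrombin time; symptoms and eosinophilia from adverse event and laboratory data; sustained elevation where serial samples exist; and the stand-alone > 8 × ULN level. Footnote any criterion that cannot be assessed.
4. Use initial as well as repeat samples for these rows, so that the 7-day repeat rule does not overwrite a qualifying value.
5. Explain in 4.5.3.1 or 4.7 why the Hy's Law definition differs from the protocol criteria.

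The cost is a few rows, a defined mapping between adverse events and laboratory dates, a check on INR availability, and possibly a higher reported count. No visit or sample is added and no clinical threshold changes; the new rows report the protocol's criteria as written.
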